8.2 Secondary study parameter(s)

The absolute decline in NRS leg pain, NRS back pain and ODI and increase in EQ5D from baseline to 2 weeks after randomization will be calculated using t-tests. The same will be done for the baseline to 4 weeks after randomization time point (using t-tests).

Perceived recovery Likert data will be dichotomized (1 and 2 is success, 3-7 is no success) and compared at 2 and 4 weeks after randomization or injection and to 14 and 26 weeks after start of severe leg pain using Chi-square tests.

The 2-week success data will be correlated to the success data after 14 weeks and subsequently for 26 weeks using Chi-square tests to make predictions. Logistic regression analysis will be used to correlate 2-week (and 4-week) success data to the absolute data for NRS leg pain, NRS back pain, ODI, increase in EQ5D at 14 and 26 weeks.

Cost effectiveness analysis:

The economic evaluation will consist of a cost-effectiveness analysis from a healthcare perspective (CEA: costs per extra patient with symptom relieve, i.e. the primary outcome measure) and a cost-utility analysis from a societal perspective (CUA: costs per QALY). Both analyses will be trial-based, using patient reports, with a half-year time horizon. Healthcare use will be valued according to the Dutch guidelines. QALYs will be calculated as the area under the utility curve, estimated using the Dutch tariff for the EQ-5D. As sensitivity analysis, QALYs will also be calculated using the VAS for quality of life (with power transformation). Average costs and patient outcome will be compared according to intention-to-treat, using net-benefit analysis, and using multiple imputation to account for missing data.

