4.4 Sample size calculation

We hypothesize that patients in the intervention group will have a mean NRS for leg pain of 4.0 on a 10-point scale at two weeks after treatment with TEI and patients in the control group will have a mean NRS for leg pain of 5.5 two weeks after randomization. A difference of 1.5 points on the NRS scale will be considered clinically relevant [17]. With a standard deviation of 2.6 (according to results of Joswig [18]), a power of 90% and a level of significance of 5% 64 patients are needed per group. This is a total of 128 patients. With a loss to follow-up of 10% we aim to include 142 patients.

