6.1.2 Secondary study parameters/endpoints

Sciatica is not only characterized by pain in the leg, but also by discomfort in functioning. Therefore the following parameters will also be evaluated.

NRS back pain: The pain intensity in the leg and the back will be measured with a 10-point horizontal Numeric Rating Scale (NRS), ranging from 0 (no pain) to 10 (worst imaginable pain). During each visit the NRS leg pain and NRS back pain will be scored. The patient is not entitled to see the pain scores indicated during previous visit(s). The NRS scores will be measured at baseline and at 1, 2, 4, 10 and 21 weeks after randomization.

Oswestry Disability Index (ODI): The functionality of the patient with a focus on walking and daily activities will be measured with the Oswestry Disability Index that is usually measured for sciatica complaints. The scale ranges from 0 (no disability) to 50 (worst disability possible). During each visit the ODI will be scored. The patient is not entitled to see the scores indicated during previous visit(s). The ODI scores will be measured at baseline and at 1, 2, 4, 10 and 21 weeks after randomization.

EuroQoL (EQ-5D): The EuroQoL (five point EQ-5D) will be used for the cost utility analysis. The tool measures five dimensions: mobility, self-care, daily activities, pain/discomfort, and anxiety/depression. Each dimension consists of one item, while three levels are distinguished (no problems, some problems, many problems). Use of the EuroQoL needs to be registered

(euroqol.org). The EuroQol scores will be measured at baseline and at 2, 10 and 21 weeks after randomization.

Quality of Life VAS (Health state utility VAS): To represent the patients perspective, utility will also be estimated using a VAS for the valuation of the patient's health state (ranging from 0 = as bad as death to 100 = perfect health), measured at baseline and at 2, 10 and 21 weeks after randomization.

Likert perceived recovery patient: To measure the perceived recovery a seven-point Likert scale will be used. The score on this scale varies from 'completely recovered' to 'worse than ever'. The Likert scores will be measured at baseline and at 1, 2, 4, 10 and 21 weeks after randomization.

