8. STATISTICAL ANALYSIS

8.1 Primary study parameter(s)

The study data will be analysed according to the intention-to –treat principle. The mean NRS for leg pain will be compared between the two groups using the unpaired t-test. This will also be done at the 4-week time point.

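### Section 8.2 tests change from baseline with t-tests and adjusts for baseline nowhere: valid, but never more precise than a baseline-adjusted comparison, apart from one degree of freedom, and clearly less precise if the baseline correlation is modest

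*Combined protocol and SAP*

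**What the plan says.** Section 8.2 takes four outcomes together: "The absolute decline in NRS leg pain, NRS back pain and ODI and increase in EQ5D from baseline to 2 weeks". The method is that the change "from baseline to 2 weeks after randomization will be calculated using t-tests". The 4-week analysis copies it: "The same will be done for the baseline to 4 weeks after randomization time point (using t-tests").

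The wording does not state that the arms are compared, or that the t-test is unpaired. Section 8.1, on the primary outcome, states both: "The mean NRS for leg pain will be compared between the two groups using the unpaired t-test". That primary test uses the follow-up score and ignores baseline.

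No baseline covariate appears in sections 8.1 to 8.3 for any between-arm comparison of a clinical outcome. The one mixed model named, in 8.3, is for macrophage counts.

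The baseline values needed for adjustment are already collected. For ODI, section 6.1.2 says: "The ODI scores will be measured at baseline and at 1, 2, 4, 10 and 21 weeks after randomization". NRS back pain follows the same schedule, and so does NRS leg pain (6.1.1). EQ-5D is scheduled only at baseline and at 2, 10 and 21 weeks, so the 4-week EQ-5D change that 8.2 calls for has no follow-up measurement.

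**The concern.** A t-test on change fixes the coefficient of the baseline score at 1. If baseline predicts follow-up only moderately, subtracting all of it adds noise. Patients enter in an acute, severe episode (sections 3 and 4.2), most cases resolve spontaneously (section 1), and the protocol expects some patients to respond to the injection and others not. A modest correlation between baseline and week 2 or 4 is therefore plausible, though the documents do not report one.

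The fixed coefficient also bears on chance imbalance. When the true regression slope is below 1, an arm that happens to start worse is credited with extra decline. The protocol cares about this: section 1 criticises the one previous acute-phase trial because its baseline pain and disability scores favoured the control group. Section 6.2 describes block randomisation with no stratification stated.

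At stake is precision on back pain, functioning and quality of life, which section 6.1.2 includes because leg pain alone does not describe sciatica.

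**Working it through.** **Inputs from section 4.4.** "A difference of 1.5 points on the NRS scale will be considered clinically relevant"; "With a standard deviation of 2.6"; "a power of 90% and a level of significance of 5% 64 patients are needed per group". These are leg-pain figures. None are given for back pain, ODI or EQ-5D, so I borrow them as a scale.

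**Assumptions.** Two-sided 5% test; a range for the correlation rho between baseline and follow-up; and three values of the baseline SD s0: 2.6 (equal to follow-up), 2.0 (smaller), and 1.2 (for leg pain, whose entry range is cut to 6–10). The follow-up SD s1 is 2.6.

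**Step 1: reproduce the plan's figure.** By the normal formula, n per arm = 2 × (1.960 + 1.282)² × 2.6² / 1.5² = 63.1, so 64 per arm and 128 in all; 128/0.9 = 142.2, against the stated 142. Power at 64 per arm is 90.4% (normal) or 89.9% (t distribution). The plan's sample size reproduces.

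**Step 2: variance of each analysis.**

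- Follow-up score only: s1²
- Change score: s0² + s1² − 2·rho·s0·s1
- Baseline-adjusted: s1²(1 − rho²)

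Change minus adjusted equals (s0 − rho·s1)², which is never negative. Apart from one degree of freedom, the change score therefore cannot be more precise than the adjusted comparison at any rho or SD ratio.

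Change is noisier than follow-up only when rho < s0/(2·s1):

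- s0 = 2.6: rho < 0.5
- s0 = 2.0: rho < 2.0/5.2 = 0.38
- s0 = 1.2: rho < 1.2/5.2 = 0.23

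At equal SDs the change variance relative to follow-up only is 2(1 − rho): 1.4 at rho 0.3, 1.0 at 0.5 and 0.6 at 0.7. The adjusted values are 0.91, 0.75 and 0.51.

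**Step 3: power.** Noncentral t, difference 1.5, 64 per arm, 126 df for change and 125 for adjusted. Worked example at rho 0.3 with equal SDs: change variance 6.76 × 1.4 = 9.46 (SD 3.08); adjusted variance 6.76 × 0.91 = 6.15 (SD 2.48).

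| Baseline SD | rho | Change | Adjusted | Gain (points) |
|---|---|---|---|---|
| 2.6 | 0.3 | 78.1% | 92.4% | 14.3 |
| 2.6 | 0.4 | 84.0% | 94.2% | 10.2 |
| 2.6 | 0.5 | 89.9% | 96.2% | 6.3 |
| 2.6 | 0.6 | 95.2% | 98.2% | 3.0 |
| 2.6 | 0.7 | 98.7% | 99.5% | 0.8 |
| 2.0 | 0.3 | 86.1% | 92.4% | 6.3 |
| 2.0 | 0.5 | 94.6% | 96.2% | 1.6 |
| 1.2 | 0.2 | 89.1% | 91.1% | 2.0 |
| 1.2 | 0.3 | 91.7% | 92.4% | 0.7 |
| 1.2 | 0.5 | 96.2% | 96.2% | 0.0 |

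Follow-up only has 89.9% throughout. A simulation with equal SDs (4,000 runs per rho) gave 78.5% vs 92.5% at rho 0.3 and 89.9% vs 96.1% at rho 0.5.

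**Step 4: chance imbalance.** The regression slope is rho·s1/s0, and the change score over-corrects only when this is below 1. At equal SDs, each point of imbalance is over-corrected by 1 − rho points. The standard error of a baseline difference is 2.6 × √(2/64) = 0.46. A one-standard-error imbalance is therefore over-corrected by 0.46 × 0.7 = 0.32 points at rho 0.3 and 0.46 × 0.5 = 0.23 at rho 0.5, against a planning difference of 1.5. With s0 = 1.2 the slope exceeds 1 above rho = 1.2/2.6 = 0.46, and the change score then under-corrects.

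**The case against.** **The test is valid.** This stands in full. Under randomisation the change-score t-test is unbiased and holds its type I error. A reader might infer that it is biased, or that a chance imbalance can manufacture or conceal an effect. The documents do not support that: the over-correction is conditional on the imbalance that happens to occur, is small against 1.5 points at one standard error, and is already contained in the larger variance. It should not be counted as a second cost on top of the power loss.

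**The size is unknown.** This also stands. The power figures rest on borrowed inputs and an assumed correlation. The argument for a low correlation comes from the course of leg pain, not back pain. Selecting patients with severe leg pain may also narrow baseline ODI, moving it towards the smaller gains. Above rho 0.5 at equal SDs, change beats ignoring baseline, so a flat claim that subtracting baseline makes matters worse would be wrong.

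**The sentence may not mean a between-arm test.** Within-arm paired tests are possible on the wording. Between-arm is the likelier reading in a 1:1 trial, coming directly after 8.1. If paired tests were meant, 8.2 would contain no between-arm comparison of mean back pain, ODI or EQ-5D, and the sentence would need rewriting anyway.

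None of this supplies a reason to prefer the change score. The baselines are collected, and no correlation or SD ratio makes it more precise than adjustment, apart from the degree of freedom.

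**Conclusion.** The point holds as one of efficiency in secondary analyses. On the leg-pain scale with equal SDs, adjustment gains about 14 percentage points of power at rho 0.3, 6 at 0.5 and under 1 at 0.7. With a baseline SD of 2.0 it gains about 6 points at 0.3 and under 2 at 0.5. For leg pain, with its restricted entry range, the gain is about 0 to 2 points, so the benefit falls mainly on back pain, ODI and EQ-5D.

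These figures show relative efficiency; they are not predicted power for those outcomes. They assume a between-arm reading, a two-sided 5% test, 64 analysed per arm and the SDs shown.

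A reader might infer that the trial is underpowered or its main result at risk. That does not follow: the primary t-test and the target of 142 patients are untouched. Separately, and without any assumption, 8.2 asks for a 4-week EQ-5D change that the schedule in 6.1.2 cannot supply.

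**What to change.** Replace the first two sentences of section 8.2 as a whole, so that leg pain keeps a stated method and the between-arm comparison is explicit:

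> NRS leg pain, NRS back pain and ODI at 2 and 4 weeks, and EQ-5D at 2 weeks, are compared between the randomised arms by linear regression of the follow-up score on arm and the baseline value of the same measure, reporting the adjusted mean difference and 95% CI; mean change per arm is descriptive.

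The 4-week EQ-5D comparison is left out because no EQ-5D is scheduled at that visit.

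Cost: a text change in one section and one degree of freedom per model. No new data, no extra patients, and no change to the primary analysis or sample size.

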2. OBJECTIVES

Primary study objective:

To study effectivity of the epidural injection with analgesic and anti-inflammatory medication to relieve the symptoms within two weeks follow up.

It will be evaluated what the average leg pain score is in both treatment arms at two weeks follow up. It will be evaluated how long the effect lasts.

The leg pain and functionality at 4 weeks after randomization will also be evaluated to get informed on the responsiveness on TEI in a somewhat later stage.

Secondary study objectives:

To evaluate the outcome of TEI in the first two weeks after randomization as a predictor of NRS leg pain at 14-16 and ca 26 weeks after onset of leg pain.

Ideally, responsiveness to TEI can predict the clinical condition at 14-16 weeks after onset of sciatica. The hypothesis is that being non-responsive to TEI within two weeks, predicts an unsatisfactory condition after 14-16 weeks of suffering. This is the category of patients that in contemporary care in the Netherlands will be offered a surgical intervention. If our hypothesis is correct, in the future, this population of patients can be offered a surgical intervention at an earlier time point.

The ca 26-week time point is chosen since in the Sciatica trial [2], both the conservative and the surgical group demonstrated comparable outcome data.

Patients in this study are included while suffering from severe leg pain for 3-8 weeks.

Presumably most patients will enter the study with 4-6 weeks of leg pain. This means that on average 10 weeks after randomization, the 14-16 week leg pain time point is reached. This means that 21 weeks after randomization the ca 26-week leg pain time point is reached.

The response in NRS leg pain, ODI and patient satisfaction at 1 week after injection and at 2 weeks after injection will be correlated to the value of these parameters at 10 and 21 weeks after randomisation.

To evaluate the cost-effectivity of analgesic/anti-inflammatory epidural injections to relieve symptoms of early sciatica.

A substantial portion of the patients in this study will eventually have an MRI of the lumbar spine. These MRIs will be evaluated according to our standard MRI evaluation protocol, that has been proven to generate additional successful conclusions and subsequent publications in the past [10-15]. Protruding disc, disc and vertebral end plate changes (MODIC) will be correlated to clinical data.

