NRS leg pain that decreases below the value of 4 (on a 10 point scale) within two weeks after TEI is documented as successful effect of TEI. NRS leg pain that remains higher than a value of 4 at a time interval of two weeks after TEI makes a patient eligible for surgery if the patient requests for surgery. If surgery is requested by the patient (either in the control or intervention group), general guidelines for timing of surgery will be conducted, meaning that the patient is encouraged to postpone surgery till 14-16 weeks after onset of pain. This decision is made using Shared Decision Making and it is possible that the patient is operated before the 14-16 week time point. The patients who are randomized cannot be operated in the first two weeks after randomization, unless sudden loss of strength or a cauda equina syndrome is reported. We expect that during these two weeks TEI will have its effect. Four

weeks after randomization the outcome parameters are measured again to be informed on the late effect of TEI. Patients will be followed up for a total duration of 21 weeks starting from the moment of randomization. Questionnaires will be filled in at baseline, 1, 2, 4, 10 and 21 weeks follow-up. A schematic overview of the study procedures is outlined in figure 1. Note that this figure does not hold into account that it is possible for patients randomized to the treatment group to receive additional injections if necessary.

[figure not shown]

Fig.1 Flow diagram of study procedures

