4.2 Inclusion criteria

In order to be eligible to participate in this study, a subject must meet all of the following criteria:

- Sciatica;
- Leg pain of 6 or more on a 10 point NRS (Numeric Rating Scale) scale with a duration of >3 and <8 weeks;
- Patient is willing to accept the possible costs for the treatment by the pain physician
- Informed consent.

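### Section 8.2 sets its late analyses at 14 and 26 weeks, timed from pain onset, while outcomes are collected at 10 and 21 weeks after randomisation; the duration of pain at entry that links the two is neither listed as baseline data nor modelled

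*Combined protocol and SAP*

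**What the plan says.** Section 8.2 names late time points in three places. Perceived recovery is compared at "14 and 26 weeks after start of severe leg pain using Chi-square tests". The prediction analysis reads "The 2-week success data will be correlated to the success data after 14 weeks and subsequently for 26 weeks using Chi-square tests to make predictions", with no origin for the 14 and 26 weeks. The logistic regression concerns "NRS leg pain, NRS back pain, ODI, increase in EQ5D at 14 and 26 weeks", again with no origin.

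Data collection runs on a different clock. Section 3 states "Questionnaires will be filled in at baseline, 1, 2, 4, 10 and 21 weeks follow-up", with follow-up counted from randomisation. Section 6.1.2 says of perceived recovery: "The Likert scores will be measured at baseline and at 1, 2, 4, 10 and 21 weeks after randomization". Sections 6.1.1 and 6.3 give the same schedule. No visit is timed from the onset of pain.

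Section 2 connects the two clocks. It states "Presumably most patients will enter the study with 4-6 weeks of leg pain" and infers that the 10-week visit is, on average, the 14-16 week point of leg pain and that the 21-week visit is the point at about 26 weeks. It then says that early response will be correlated with values at 10 and 21 weeks after randomisation. Eligibility is wider than the presumed entry: section 4.2 admits leg pain "with a duration of >3 and <8 weeks". The baseline list in section 6.1.3 does not include duration of the current episode, and no model in section 8.2 includes it.

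**The concern.** The analysis section disagrees with the visit schedule and with the objectives about when the late outcomes are measured. It also shortens the ranges in section 2 to the single values 14 and 26, and gives no window or rule for assigning a visit to a time since onset. Where no origin is stated, an analyst could take 14 weeks as counted from randomisation, where there is no visit, or could choose a window after seeing the data.

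The prediction hypothesis gives this weight. Section 2 proposes that non-response within two weeks foretells a poor condition at 14-16 weeks of pain, and intends the result to inform when surgery might be offered in future. Section 3 says that patients who ask for surgery are encouraged to wait until 14-16 weeks after onset, although earlier surgery remains possible. A 10-week visit may therefore fall before, inside or after that period, depending on how long the patient had been in pain at entry. Duration at entry thus bears on whether the outcome is recorded before or after surgery, yet the plan neither lists it as a baseline variable nor adjusts for it.

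**Working it through.** **Inputs.** Entry at more than 3 and less than 8 weeks of pain (section 4.2); presumed entry for most patients at 4-6 weeks (section 2); late visits at 10 and 21 weeks after randomisation (sections 3 and 6.1.2); analysis points at 14 and 26 weeks (section 8.2).

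**Formula.** Weeks since onset at a visit = weeks of pain at entry + weeks since randomisation.

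**The plan's own mapping.** Entry at 4-6 weeks gives 4 + 10 = 14 to 6 + 10 = 16, and 4 + 21 = 25 to 6 + 21 = 27, with midpoint 26. Section 2 is reproduced.

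**Full eligibility range** (the end values 3 and 8 are limits):

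| Weeks of pain at entry | At the 10-week visit | At the 21-week visit |
|---|---|---|
| 3 | 13 | 24 |
| 4 | 14 | 25 |
| 5 | 15 | 26 |
| 6 | 16 | 27 |
| 7 | 17 | 28 |
| 8 | 18 | 29 |

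Each visit covers a span of 8 - 3 = 5 weeks since onset. An exact 14 needs entry at 4 weeks and an exact 26 needs entry at 5 weeks. The visits are 21 - 10 = 11 weeks apart and the stated points 26 - 14 = 12 weeks apart, so no patient can meet both exactly.

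**Share of patients near the stated points.** The documents give no distribution of entry times, so two are assumed: uniform over 3-8 weeks, and uniform over 4-6 weeks. The windows of one week either side are also assumptions.

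| Condition | Entry needed (weeks) | Uniform 3-8 | Uniform 4-6 |
|---|---|---|---|
| 10-week visit inside 14-16 weeks | 4-6 | 2/5 = 40% | 2/2 = 100% |
| 10-week visit within 1 week of 14 | 3-5 | 2/5 = 40% | 1/2 = 50% |
| 21-week visit within 1 week of 26 | 4-6 | 2/5 = 40% | 2/2 = 100% |
| Both within 1 week | 4-5 | 1/5 = 20% | 1/2 = 50% |

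If 80% of patients enter at 4-6 weeks (a further assumption), 80% of 10-week visits fall inside 14-16 weeks.

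Even under presumed entry, the average 10-week visit is at 5 + 10 = 15 weeks since onset. The 14 in section 8.2 is therefore the early edge of the range in section 2, not its centre.

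**The case against.** The best defence is that section 2 already resolves the matter. It explains why weeks 10 and 21 were chosen, treats them as approximations, and words the prediction analysis at 10 and 21 weeks after randomisation. Since no other late data will exist, 14 and 26 weeks can be read as shorthand for those visits. On the protocol's own expectation, most patients are then measured inside the intended period.

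Much of this stands. A reader might infer from section 8.2 that almost no patient will have data at the stated times, or that the late outcomes will be missing. The documents do not support that. It follows only if 14 and 26 are read as exact days, whereas section 2 speaks of a range and an approximate value, and every patient has scheduled 10- and 21-week questionnaires.

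A reader might also infer that leaving out symptom duration biases the comparison between arms. It does not: randomisation balances duration in expectation. The case for the covariate rests on the prediction analysis, which relates early to late status within patients and gains no such protection.

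The defence does not explain why the analysis section departs from the objectives. Nor does it cover patients who enter outside 4-6 weeks: eligibility admits them, and the plan's expectation about entry is only presumed.

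**Conclusion.** The point holds as an inconsistency of time origin between the analysis section on one side and the visit schedule and objectives on the other, together with an unrecorded linking variable. Late outcomes will be observed at 13-18 and 24-29 weeks since onset over the eligible range, and at 14-16 and 25-27 weeks for the presumed entrants. How many 10-week visits fall inside 14-16 weeks depends on recruitment: from 40% to 100% under the two assumed entry distributions. The consequence is limited to the secondary late comparison and the prediction analyses, whose conclusions would otherwise be stated for a time since onset that some patients' visits do not represent. The two-week primary analysis and the sample size do not depend on it. It should be corrected, at little cost, before analysis.

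**What to change.** 1. In section 8.2, replace 14 and 26 weeks with 10 and 21 weeks after randomisation in all three places, so that it agrees with sections 2, 3 and 6.
2. Add weeks since onset of leg pain at randomisation to the baseline list in section 6.1.3. It has to be assessed for eligibility anyway.
3. Include it as a covariate in the prediction regression. The chi-square tests cannot carry it, so the regression should support the predictive claim.
4. Word the conclusions as applying to the 10- and 21-week visits, and report the observed range of weeks since onset at each, so that readers can judge how well they represent 14-16 and about 26 weeks.

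The cost is a change of wording, one recorded field and one extra model term. No visit or patient is added.

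### Section 8.2 relates 2-week response to later success without handling surgery in between, which can dilute the predictor analysis, most at week 21; it also names logistic regression for continuous later scores

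*Combined protocol and SAP*

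**What the plan says.** Section 2 sets the secondary objective: "To evaluate the outcome of TEI in the first two weeks after randomization as a predictor of NRS leg pain". The time points named are 14-16 and about 26 weeks after onset, which it places at roughly 10 and 21 weeks after randomisation. The hypothesis is that non-response within two weeks predicts a poor condition at 14-16 weeks. If so, such patients could in future be offered surgery earlier.

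Section 8.2 gives two analyses for this. The binary one is: "The 2-week success data will be correlated to the success data after 14 weeks and subsequently for 26 weeks using Chi-square tests". The other is: "Logistic regression analysis will be used to correlate 2-week (and 4-week) success data to the absolute data for NRS leg pain", and likewise for back pain, ODI and EQ-5D.

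Section 3 links the predictor to surgery on request. Of the leg-pain score it says: "remains higher than a value of 4 at a time interval of two weeks after TEI makes a patient eligible for surgery". On timing, "the patient is encouraged to postpone surgery till 14-16 weeks after onset of pain", but "it is possible that the patient is operated before the 14-16 week time point".

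Success has two candidate meanings. Section 3 has "NRS leg pain that decreases below the value of 4 (on a 10 point scale) within two weeks after TEI is documented as successful", and the Summary uses the same NRS cut-off of 4 at weeks 2, 10 and 21. Section 8.2 has "Perceived recovery Likert data will be dichotomized (1 and 2 is success, 3-7 is no success".

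Section 8.1 applies intention-to-treat. Sections 6.5 and 6.6 class patients who refuse TEI or are withdrawn from treatment as cross-overs. None of these mentions surgery.

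**The concern.** The patients predicted to do badly are the ones given access to an operation that may remove the bad outcome before it is measured. If a non-responder is operated on, recovers and is scored as recorded, that patient counts against the hypothesis even if he or she would have done badly without surgery. A true link then becomes harder to show. A weak result, particularly at week 21, may partly reflect successful surgery. Because no rule is set in advance, one could also be chosen after the data are seen, and the rules give very different answers.

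The second issue is direction. Logistic regression needs a binary dependent variable. With continuous later scores, the only binary variable left is 2-week success, so the model runs from the later score back to the early response. The objective runs the other way.

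**Working it through.** The documents give no power or sample size for the predictor analysis, so there is no planned figure to reproduce. The group size of 64 in section 4.4 is used as an input. It does reproduce: 2 × (1.960 + 1.282)² × 2.6² / 1.5² = 63.1, rounded up to 64.

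**1. Timing, from sections 2, 3 and 4.2.** Entry is at 3-8 weeks of pain. Surgery at 14-16 weeks after onset therefore falls between 14 − 8 = 6 and 16 − 3 = 13 weeks after randomisation, always before week 21. It falls before week 10 only if 14 − entry < 10 (entry after more than 4 weeks of pain) or 16 − entry < 10 (more than 6 weeks), or if the patient is operated on sooner, which section 3 allows.

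**2. Groups.** The analysis is taken to be within the TEI arm. Section 1 cites 33% non-responders: 0.33 × 64 = 21.1, so 21 non-responders and 43 responders.

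**3. Assumed rates, none from the documents.** Unsatisfactory without surgery: p = 0.70 in non-responders and 0.20 in responders, a 50-point difference. Surgical failure f = 0.20. A share o of non-responders is operated before the visit, and no responders.

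**4. Scores as recorded.** The unsatisfactory share in non-responders becomes:
- (a) p − o + f·o, if only those who would have failed are operated;
- (b) p(1 − o) + f·o, if the operated are a random draw.

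Exact power of the uncorrected two-sided 5% chi-square test against 0.20 in responders:

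| o | (a) share | (a) power | (b) share | (b) power |
|---|---|---|---|---|
| 0 | 0.70 | 98.1% | 0.70 | 98.1% |
| 0.10 | 0.62 | 92.5% | 0.65 | 95.3% |
| 0.20 | 0.54 | 79.5% | 0.60 | 90.0% |
| 0.40 | 0.38 | 35.0% | 0.50 | 70.0% |

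So at o = 0.40 the 50 points shrink to 18 (a) or 30 (b).

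**5. Other assumptions.**
- Surgical failure f = 0.40, o = 0.40: power 58.8% (a) or 87.0% (b).
- Weaker link, 0.60 against 0.25, f = 0.20: power is 79.0% without surgery, 58.3-69.4% at o = 0.10 and 6.3-35.1% at o = 0.40.
- An even split of 32 and 32 (suggested by the planned TEI mean of 4.0), first scenario: 95.0-97.2% at o = 0.10 and 36.1-73.4% at o = 0.40.

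**6. Surgery counted as unsatisfactory.** The non-responder share is p under (a) and p(1 − o) + o under (b). At o = 0.40 these are 0.70 and 0.82, or 50-62 points. With no true link (0.30 in both groups) and o = 0.40 at random: 0.30 × 0.60 + 0.40 = 0.58 against 0.30, a false 28-point difference.

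**7. The two versions need not bracket the truth.** Let 10% of responders also be operated, at random, with o = 0.20 and draw (b). As recorded: 0.60 − (0.20 × 0.90 + 0.20 × 0.10) = 0.40. Surgery as unsatisfactory: 0.76 − (0.20 × 0.90 + 0.10) = 0.48. Both lie below the true 0.50.

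**8. Linear model.** If the SD of 2.6 in section 4.4 also holds later, the 95% CI half-width for the later NRS difference between 2-week groups is t(62) × 2.6 × √(1/21 + 1/43) = 1.38 points.

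**The case against.** The strongest reply is that the plan has a default. Intention-to-treat with no recoding means scores as recorded, and a sensible main analysis would use them too. That is fair, but it is the version that dilutes, and intention-to-treat governs the comparison of arms rather than how surgery enters a prediction within patients.

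Second, the hypothesis with a clinical consequence concerns 14-16 weeks after onset, about week 10, which is the less exposed visit. This stands and limits the point: the loss there is small if few are operated by then and the link is strong. Week 21 is still a stated predictor time point.

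Third, a reader might infer that a weak result could never be told apart from successful surgery. The documents do not support that. Section 10.1 already collects lumbar surgery data from the hospital system, so operated patients can be tabulated by 2-week response. What is missing is a plan to do so.

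Fourth, the sentence before the predictor analysis defines success by the Likert score, so the ambiguity is softer than it first looks. Yet the Summary and section 3 use NRS below 4, and the objective is about NRS leg pain.

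Fifth, logistic regression with 2-week success as the dependent variable is a valid test of association, and the chi-square test already addresses the binary hypothesis. Calling the model invalid would go too far; it simply does not predict the later score.

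**Conclusion.** The point holds for a secondary objective and should be addressed. Section 8.2 leaves surgery between the 2-week and later visits unhandled while section 3 ties surgery to the 2-week result, so the planned analysis can understate a true association. Week 21 is most exposed and week 10 only partly. The logistic model runs opposite to the objective.

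The size cannot be fixed from the documents. In the first scenario, power goes from 98% to 92-95% with 10% of non-responders operated and to 35-70% with 40%. A weaker link makes the loss larger, and less successful surgery makes it smaller. A reader might take the 40% surgery rate quoted in section 1 as the expected share. It describes the whole conservative arm of another trial and does not estimate surgery among TEI non-responders.

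Nor does it follow that the trial's main result is in doubt. The primary comparison is at two weeks, and section 3 bars surgery in that period except for sudden loss of strength or cauda equina syndrome.

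**What to change.** 1. **Model and definition.** Replace the logistic model for the later NRS, ODI and EQ-5D with linear regression of the week-10 and week-21 scores on 2-week response. Keep chi-square or logistic regression for binary later success, and report positive and negative predictive values with 95% CIs. Use one success definition at both the early and the later visits: NRS below 4 for the NRS-based hypothesis, with Likert 1-2 as a second version.

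2. **Surgery.** For weeks 10 and 21 separately, report the number operated before the visit by 2-week response. Report the binary analysis with scores as recorded and, as a sensitivity analysis, with prior surgery counted as unsatisfactory. For the continuous scores, the sensitivity version uses the last score before surgery in operated patients.

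3. **Interpretation.** State in advance that the as-recorded version can dilute the association, that the sensitivity versions can inflate it, that neither stands alone, and that the two need not lie on either side of the truth.

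The cost is analysis-plan wording and making sure the date of surgery is extracted with the surgery data already collected under section 10.1. The downside is somewhat more analysis and a less clear-cut conclusion if the versions differ. Running the same analysis in the control arm, to separate natural improvement from response to TEI, is an optional exploratory extra and not part of this defect.
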